### **3.0 Study Endpoints/Events/Outcomes**

- 3.1 Primary Endpoint/Event/Outcome: *Change in amplitude of AEP as recorded by the EEG. Change in AEP is a proxy for brain plasticity.*
- 3.2 Secondary Endpoint(s)/Event(s)/Outcome(s): N/A

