4.3 Biosafety: N/A

4.4 Stem Cells: N/A

## 5.0 Procedures Involved

5.1 Study Design: *The study will be conducted in a blinded, within-groups design involving two separate study sessions. The two sessions will consist of simultaneous tDCS and EEG recording. Each participant will receive both active and sham tDCS over the course of the two sessions (but not within a single session). Order of stimulation type will be counterbalanced across participants. The two sessions will be spaced at least 24 hours apart. The consent process will be done at the first study session. The primary outcome measure will be the difference in the amplitude of the ERP's (specifically the N100 component) recorded before and after tDCS. This difference is reflective of the capacity of the sensory cortex to support synaptic plasticity.*

5.2 Study Procedures:

- Screening Visit: *The screening process will happen over email or phone (depending on how participant makes contact). Potential participants will be provided with information about the study using an established script and will be asked a series of questions to determine if they meet basic inclusion/exclusion criteria (see below). They will be told about the basic aims of the study, and those interested in participating will be scheduled for the study.*
- Study visits: *Visits will take place at our [name] offices, the Ambulatory Research Center (ARC) at the department of Psychiatry, or at the clinical spaces at our St. Louis Park location. At the first study session, the participants will complete the informed consent process. The participant will also be told that this is not a treatment study and no benefits to the participant are expected from the study. After, and if, they complete the process, the participant will fill out the tDCS Side Effect Questionnaire (TSEQ), and the Edinburgh Handedness Inventory. These two brief questionnaires ask about potential side-effects of tDCS and the subject's handedness respectively. After the paperwork has been completed, the participant will undergo EEG and either active or sham tDCS (see embedded figure). The stimulation and the recording will be provided using the StarStim Neurostimulator (Neuroelectrics, Inc.). This device has been approved for use in research in the United*

PROTOCOL TITLE:

VERSION DATE:

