*States without an investigational device exemption due to meeting criteria for non-significant risk. The device utilizes standard Ag/Cl electrodes embedded in an easy to use neoprene cap. A small amount of conductive gel is applied to each electrode before insertion into the head cap. Electrodes will be positioned on the subject's scalp according to the international 10/20 electrode placement system. During EEG recording, all electrodes will be utilized to record brain signal. The session will begin with EEG recording while the participant engages in a visual search task. Immediately after, either a passive Auditory Oddball paradigm or a passive Visual Oddball paradigm (these tasks are described in detail in the instruments section) will begin. They will be seated in front of a monitor as they observe visual stimuli or will be wearing insert headphones through which auditory stimuli will be delivered. After the first Oddball task, simultaneous EEG and tDCS will commence for a period of 10 min. During simultaneous EEG and tDCS, two electrodes will be used to deliver stimulation, while the remaining electrodes continue to record EEG. The two stimulation electrodes will be positioned bilaterally over the auditory cortex (T3/T4). In the anodal group the device will deliver 1mA of current through each stimulating electrode. The current is initiated in a ramp like fashion over a 10 sec period from 0mA to 1mA. Once at 1mA, the current is held constant for the duration of the session. Should the participant not be able to tolerate a current of 1mA due to pain or irritation, the current will be decreased down to a minimum of 0.5mA. If 0.5 mA is still not tolerable, the participant will be removed from the study. The sham procedure involves only 40 sec stimulation at 1mA and then drops to 0mA with 15ms pulses every 550ms. This simulates the tingling sensations that are often associated with active stimulation. 15min into the stimulation session the sensory tetanus will commence. The auditory tetanus involves the presentation of a 1000Hz tone at a rate of 13Hz for a period of approximately 5min. The visual tetanus involves the presentation of the visual stimulus (either a horizontal or vertical grating) at a rate of 9Hz. Sensory tetanus and tDCS will end at the same time. Briefly after tetanus and tDCS, the participants will perform the second oddball task as well as a final visual search task. 30 min after the cessation of tDCS, a final oddball task will be conducted. After the completion of the EEG recording, the head cap will be removed and the participant will be given the opportunity to wash their hair (towels and shampoo provided). The two study sessions will be identical, differing only in type of tDCS applied (sham or active).*

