13.3 Risks to Others: **N/A**

## **14.0 Potential Benefits to Participants**

14.1 Potential Benefits: *No benefits expected for participating in the study*

## **15.0 Statistical Considerations**

15.1 Data Analysis Plan: *Data analyses will include traditional statistical analyses for within-groups differences in EEG neuroimaging data.*

15.2 Power Analysis: *35 participants in a within-groups design will provide the statistical power ( $1 - \beta = 0.80$ ) necessary to detect effect sizes greater than  $d' = 0.450$ . Based on the large effect sizes ( $d' > 0.68$ ) reported by Clapp et al. (2005) we expect to be sufficiently powered with the aforementioned sample size.*

15.3 Statistical Analysis: *Data will be analyzed in a 2-way ANOVA with correction for multiple comparisons*

15.4 Data Integrity: *EEG data will be subjected to standard quality control measures (both automated and manual) including measuring and controlling for artefacts.*

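### The primary change-score analysis fixes the slope on each session's baseline N100 at 1; estimating that slope would usually gain power from recordings already planned

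*Combined protocol and SAP*

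**What the plan says.** Section 3.1 gives the primary endpoint as "Change in amplitude of AEP as recorded by the EEG". Section 5.1 narrows it: "The primary outcome measure will be the difference in the amplitude of the ERP's (specifically the N100 component) recorded before and after tDCS". The whole statistical model is one sentence in section 15.3: "Data will be analyzed in a 2-way ANOVA with correction for multiple comparisons". Section 15.1 adds only "Data analyses will include traditional statistical analyses for within-groups differences in EEG neuroimaging data". Neither sentence names the ANOVA factors, a covariate or a baseline term.

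The design is a two-session crossover with counterbalanced order and at least 24 hours between sessions (section 5.1). Section 5.2 places an oddball recording before stimulation: "After the first Oddball task, simultaneous EEG and tDCS will commence for a period of 10 min". It schedules two more oddball recordings, one shortly after tDCS and one 30 minutes after it ends, and says the sessions differ only in the type of stimulation. Each participant therefore has a pre-tDCS recording under both conditions. Section 5.2 allows an auditory or a visual oddball task, so an auditory N100 baseline exists only where the auditory task was used.

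On power, section 15.2 says "35 participants in a within-groups design will provide the statistical power" of 0.80 to detect effects above d' = 0.450, and expects d' above 0.68. It gives no alpha, sidedness, SD or correlation. Section 2.2 lists no preliminary data.

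**The concern.** Pairing within participants removes stable differences between people. It does not remove variation in N100 from one session to the other. What remains at baseline is each participant's active-minus-sham difference before stimulation. If that difference carries over only partly into the post-tDCS difference, subtracting all of it puts noise into the primary contrast.

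Precision is at stake, not validity. With 35 completers, the same recordings could give a narrower interval for the active-sham contrast if the slope were estimated.

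**Working it through.** **Inputs.** From section 15.2: n = 35, d' = 0.450, expected d' above 0.68, stated power 0.80. Assumed, because the documents do not say: alpha 0.05 two-sided; d' is the mean divided by the SD of the within-person difference in changes; r from 0 to 0.95.

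**Step 1: the plan's own figure.** The normal approximation is Φ(0.45 × √35 − 1.96) = Φ(2.66 − 1.96) = Φ(0.70), about 0.76. The exact paired t-test (34 df) gives 0.735, and a one-sided 0.05 test gives 0.832. Neither is the stated 0.80. That mismatch is a separate matter; 0.735 is the reference value here.

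**Step 2: what the ANOVA does.** For each participant let D_pre be pre(active) − pre(sham) and D_post be post(active) − post(sham). In a stimulation-by-time ANOVA with two time levels, the interaction tests whether the mean of D_post − D_pre is zero. This is a paired t-test of change scores, with the slope of D_post on D_pre set to 1.

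**Step 3: variance.** Let V be the variance of D_pre, k the ratio of the SD of D_post to that of D_pre, and r their correlation.

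- Change score: V(1 + k² − 2rk)
- Slope estimated, large samples: V k²(1 − r²)
- The first minus the second is V(1 − rk)². This is zero only when the true slope rk equals 1.

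With k = 1 the ratio is V(1 − r²) / [2V(1 − r)] = (1 + r)/2.

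**Step 4: power at n = 35, effect 0.45, k = 1.** Estimating a baseline slope and an order effect leaves 32 df. Estimating the baseline slope inflates the variance by about 1 + 1/31 = 1.032. The noncentrality is 0.45 × √35 / √(ratio × 1.032). At r = 0.5 this is 2.662 / √(0.75 × 1.032) = 3.03, which gives power 0.835.

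| r | variance ratio (1 + r)/2 | power, change score | power, slope estimated |
|---|---|---|---|
| 0 | 0.50 | 0.735 | 0.949 |
| 0.3 | 0.65 | 0.735 | 0.883 |
| 0.5 | 0.75 | 0.735 | 0.835 |
| 0.7 | 0.85 | 0.735 | 0.787 |
| 0.9 | 0.95 | 0.735 | 0.741 |
| 0.95 | 0.975 | 0.735 | 0.730 |

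Simulation of the regression with a centred order term (40,000 runs per value) agrees to within about half a point. Type I error was between 0.048 and 0.052 for both methods.

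**Step 5: unequal variances.** At r = 0.5 and k = 1.2 the ratio is 1.44 × 0.75 / (1 + 1.44 − 1.2) = 1.08/1.24 = 0.87, and simulated power is 0.78. At r = 0.5 and k = 1.5 it is 1.6875/1.75 = 0.96, with power 0.73. At r = 0.8 and k = 1.25 the slope is exactly 1, the ratio is 0.5625/0.5625 = 1, and power is 0.72. The largest loss in the scenarios run was about 1.5 points.

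**Step 6: at the expected effect.** With d' = 0.68 the change-score test already has power 0.974. At r = 0.5 estimating the slope takes it to about 0.99.

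**The case against.** The strongest reply is that this is an optimisation. The change score is valid, it is the construct the protocol declares, and the size of any gain depends on an r and on variances that nobody can read from the documents. Pre and post recordings share one session and one cap, which could push r up to where the gain is small. All of this stands, and it limits the claim to efficiency.

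It does not remove the advice. Both pre-tDCS recordings precede that session's stimulation, so with counterbalanced order and no carry-over the expected D_pre is zero. The regression intercept and the mean difference in changes then estimate the same quantity. Carry-over after a gap as short as 24 hours would disturb either analysis.

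Four stronger readings might be inferred, and the documents do not support them:

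- **The plan ignores baseline.** It does not: the change score subtracts each session's own baseline. Only an estimated slope is missing.
- **Adjustment gains power for every r below 1.** That needs equal variances and a large sample. At n = 35 the cost of estimation cancels the gain near r = 0.95, and a larger post-tDCS variance can cancel it at lower r.
- **The power statement leaves no room.** Section 15.2 expects d' above 0.68, where change-score power is about 0.97. Whether that benchmark is sound is a separate question.
- **Section 15.3 commits to the two-level ANOVA.** It names no factors. With three oddball recordings, time could have three levels, and the interaction would then have 2 df and not be a single paired test. On no reading, however, does the section contain a baseline covariate.

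**Conclusion.** The point holds as a matter of efficiency. If section 15.3 means stimulation by time with one post recording, the primary test fixes at 1 a slope that the planned recordings could estimate. At an effect of 0.45 SD of the difference in changes, the gain is about 21 power points at r = 0, 10 at r = 0.5, 5 at r = 0.7, under 1 at r = 0.9 and none by r = 0.95. Where the true slope is near 1 the loss is at most about 1.5 points. If the effect is as large as the expected 0.68, at most about 3 points remain to be gained.

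These figures assume 35 completers, two-sided 0.05, equal pre and post variances except where stated, normal data and an auditory pre-tDCS recording in both sessions. The direction is well supported for slopes clearly below 1. The size cannot be fixed from the documents. Nothing here shows bias or an inflated error rate in the planned test.

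**What to change.** In section 15.3, prespecify the primary analysis as a linear regression across participants:

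- **Outcome:** the active-minus-sham difference in post-tDCS N100 at one named recording, either shortly after or 30 minutes after tDCS.
- **Covariate:** the active-minus-sham difference in pre-tDCS N100. Do not centre it on its sample mean, so that the intercept refers to a zero baseline difference.
- **Order:** active first or sham first, coded as a centred term.
- **Test:** the intercept, at a stated alpha and sidedness.

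Using within-person differences for both outcome and covariate keeps between-person baseline effects out of the slope. Keep the change-score ANOVA, with its factors and time levels named, as a sensitivity analysis.

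The cost is analysis-plan wording and two degrees of freedom (34 to 32), one for the baseline slope and one for order. No new recordings, visits or participants are needed.

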8.2 Exclusion Criteria: *Exclusion criteria are listed below:*

- *History or tDCS or other cortical energy exposure within past 12 months*
- *History of seizures or epilepsy*
- *Cranial metallic plates/screws*
- *Implanted devices*
- *History of craniotomy*
- *History of eczema on scalp*
- *Bipolar disorder or Depression diagnosis*
- *Cornrows or dreadlocked hair*
- *Impaired hearing*

8.3 Screening: *The screening process will happen over email or phone (depending on how participant makes contact). Potential participants will*

PROTOCOL TITLE:

VERSION DATE:

*be provided with information about the study using an established script and will be asked a series Health & Biological/Medical Application Form 7 of questions to determine if they meet basic inclusion/exclusion criteria.*

*They will be told about the basic aims of the study, and those interested in participating will be scheduled for the study. At the study visit, the participants will first complete the informed consent process*

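### As section 5.2 is written, the only side-effect form (TSEQ) is completed before stimulation, and no side-effect form or skin check is scheduled after tDCS in either session

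*Combined protocol and SAP*

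**What the plan says.** Section 5.2 (Study visits) sets the order for the first session. After consent, "the participant will fill out the tDCS Side Effect Questionnaire (TSEQ), and the Edinburgh Handedness Inventory". The next step is conditional on that: "After the paperwork has been completed, the participant will undergo EEG and either active or sham tDCS". The sentence ends by pointing to an embedded figure, which is not reproduced in the text available. The same section says of the oddball tasks that "these tasks are described in detail in the instruments section"; the table of contents lists no such section.

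After stimulation, the section describes a second oddball task and a visual search, and then "30 min after the cessation of tDCS, a final oddball task will be conducted". The session closes with "After the completion of the EEG recording, the head cap will be removed" and an offer to wash the hair. For the second visit it says "The two study sessions will be identical, differing only in type of tDCS applied (sham or active)". Section 5.1 adds that "The two sessions will be spaced at least 24 hours apart".

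Sections 5.2 (Precautions Taken) and 13.1 give sores at the electrode site, headache that impairs functioning and worsening psychosis as reasons to discontinue. Section 13.1 lists itching, headache, fatigue and nausea as mild effects. Section 8.2 excludes people with "History or tDCS or other cortical energy exposure within past 12 months".

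**The concern.** A form completed before exposure cannot record the effects of that exposure. Section 5.2 describes the TSEQ as asking about possible side effects of tDCS, so its natural place is after stimulation, or both before and after. Placed only before, it gives background symptoms and nothing else.

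Two things are at stake, both modest. First, the protocol undertakes to discontinue participants for sores or impairing headache but schedules no step at which anyone asks or looks. Second, every completer receives both active and sham stimulation, a good setting for a within-person description of tolerability. Without a solicited rating under each condition that description cannot be made systematically, and a low count of mild effects could simply mean that nobody asked.

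**Working it through.** The plan gives no figure for this point, so the check is one of order, followed by simple counts.

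**Order of events in session 1 (section 5.2)**

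1. Consent.
2. TSEQ and handedness form.
3. EEG with visual search.
4. First oddball task.
5. tDCS (active or sham), with the sensory tetanus.
6. Second oddball task and visual search.
7. Final oddball task, 30 minutes after tDCS ends.
8. Cap removal and optional hair wash.

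The TSEQ is at step 2 and stimulation at step 5. Steps 6 to 8 contain no side-effect form and no skin check. Sections 4.2, 12, 13, 15, 17, 18 and 23 add no other side-effect instrument or scheduled inspection.

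**Could the step 2 form capture study effects?** Not at session 1: no study stimulation has been given, and section 8.2 excludes tDCS in the preceding 12 months. For session 2 there are two readings:

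- The TSEQ belongs with the consent paperwork and is completed once, at session 1. It then captures no study effects.
- Identical sessions means that it is repeated before stimulation at session 2. It could then pick up session 1 effects, recalled at least 24 hours later. Session 2 effects would still not be asked about.

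On neither reading is there an assessment after stimulation within the same session.

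**Number of sessions concerned (section 10.1: up to 80 consented, goal of 35 completers)**

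- Completers: 35 × 2 = 70 sessions.
- Upper figure, assuming that each of the other 80 − 35 = 45 people has one session: 70 + 45 = 115.
- Scheduled post-stimulation forms or skin checks in the text: 0 of 70, or 0 of up to 115.

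**Burden of one added form per session**

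- Forms: 70 to 115.
- Time per form is not given; 2 to 5 minutes is assumed. Lowest total: 70 × 2 = 140 minutes, or 2.3 hours. Highest total: 115 × 5 = 575 minutes, or 9.6 hours.
- Skin look, at an assumed 1 minute per session: 70 to 115 minutes, or 1.2 to 1.9 hours.

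**The case against.** The strongest objection is that the sentence fixing the order refers to a figure that cannot be seen. It may well be the session schedule and may show a TSEQ after stimulation. What is lost in reproduction is not missing from the plan. This stands as a reason to confirm before changing anything. It does not remove the point, because the prose order is explicit and a reader following 5.2 would give the form before stimulation only.

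A reader might infer that side effects would go undetected. The documents do not support that. Participants may stop at any time; the device can cut out; current can be reduced to 0.5 mA, failing which the participant is removed (4.2, 5.2). Section 18.1 tells participants to speak up about discomfort and offers a chance to discontinue before each session. The principal investigator monitors safety (17.1), adverse effects are reviewed weekly (23.1), and events go to the IRB (5.2). Participants also remain on site for at least 30 minutes after tDCS. Sores and disabling headache would probably come to light by these routes. None of them is a scheduled post-stimulation assessment, so the gap that remains mainly concerns mild effects.

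A reader might also take section 6.2, which limits stored data to EEG recordings, to mean that TSEQ answers would be discarded. That section sits under data banking, and 16.1 provides for paper records and a research database, so 6.2 need not change.

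Finally, tolerability is not a study objective: the only endpoint is the AEP change, and no planned inference needs a side-effect comparison. That is correct, and it is why the priority is low.

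**Conclusion.** The point holds as a low-priority matter for the sponsor to consider. On the text of 5.2, the only side-effect form precedes stimulation and nothing is scheduled after it in either session. Mild effects are therefore recorded only if volunteered or noticed, and cannot be compared systematically between active and sham. Volunteered events, current reductions and removals can still be tabulated by condition.

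This rests on the prose of 5.2 being the operative schedule; a different timing in the embedded figure would reduce it to a one-sentence clarification. The count of 70 sessions assumes that the target of 35 completers is met, and 115 assumes one session for each other consented person.

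The documents give no side-effect rate and no share of effects that would be volunteered, so they cannot show how many effects would be missed. The N100 analysis is unaffected, and exposure is 1 mA through each stimulating electrode, in healthy adults, from a device classed as non-significant risk.

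**What to change.** First check the embedded figure and any instrument description. If a TSEQ already follows stimulation, say so in 5.2; nothing more is needed on timing.

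If it is only pre-stimulation:

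- Keep the present TSEQ as a baseline and repeat the same form, unaltered, once per session after the 30-minute oddball task.
- At cap removal, look briefly at the skin under the stimulating electrodes (T3/T4) and the supraorbital return electrodes described in 4.2.
- Add a line to section 15 stating that responses will be reported descriptively by condition for everyone who received any stimulation, not only completers, alongside volunteered events, current reductions and removals.

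No new instrument is needed. The cost is 70 to 115 extra brief forms and a minute or so per skin look, a few minutes per session on the assumed timings, plus short edits to 5.2 and 15. The form follows the last EEG task, so it cannot alter that session's N100.

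The main downside is that asking about sensations after session 1 may prompt some participants to guess their condition before session 2. This is probably small, but the documents give no means of sizing it. Counterbalancing the order would balance a shift common to both orders, but not one that depends on the condition guessed.

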*SSP is a Non-Invasive Measure of Synaptic Plasticity: Recently developed techniques utilizing the EEG now enable the non-invasive interrogation of synaptic plasticity in the human cortex. As demonstrated first by Clapp et al., (2005), and since then by others (Teyler et al., 2005; Zaehle et al., 2007), it is possible to induce LTP in the human sensory cortices by the rapid presentation of sensory stimuli. It has been shown that a rapidly presented checkerboard pattern (a photic tetanus) can induce long lasting changes in evoked potentials (Teyler et al., 2005), spectral features (Clapp et al., 2006a), and hemodynamic response (Clapp et al., 2005a) in the visual cortex. Similar findings have been reported in the auditory cortex with rapid presentation of auditory tones (Clapp et al., 2005b). Here, the N100 component of the auditory evoked potential (AEP) was potentiated post auditory tetanus. The N100 component is a negative peak that emerges just anterior of the Cz electrode and is thought to emanate from the bilateral superior temporal gyri (Ford et al., 2016; Zaehle et al., 2007). The potentiation of the AEP post tetanus was independent of arousal state and persisted for over an hour without decrease. Studies of SSP in rats demonstrate that the potentiation effect is long lasting, NMDAR dependent and input specific, supporting the theory that SSP is indeed inducing LTP (Clapp et al., 2006b). This paradigm is thus a close parallel to the high frequency electrical stimulation that is used to induce LTP in animal and tissue models. These properties make SSP an ideal translational tool for*

PROTOCOL TITLE:

VERSION DATE:

*recapitulating the work done in models regarding the effects of tDCS on neural plasticity. To date no one has used SSP to analyze tDCS effects.*

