
- Precautions Taken: *tDCS is considered to be a safe brain stimulation technique that rarely result in adverse events. There is currently no evidence of serious side-effects. We will discontinue any participant who experiences sores at the tDCS administration site, headaches that*

PROTOCOL TITLE:

VERSION DATE:

*impair global functioning, and worsening psychosis. Mild side-effects typically resolve upon discontinuation tDCS. The participant may choose to discontinue stimulation at any time during the session if experiencing discomfort or side effects. No other risks are anticipated. Nonetheless, in order to minimize risks, study staff will be using standards of administration that have been shown to be safe in numerous other studies and across more than 2000 studies (Liebetanz et al., 2009; Nitsche et al., 2007; Poreisz, Boros, Antal, & Paulus, 2007) using tDCS; this includes length of administration, magnitude of the current, size of electrode sponges used, and method of applying stimulation. Any unanticipated problems or adverse events will be reported according the University of Minnesota IRB standard operating procedure. 2. Participants will be informed that they are not required to answer any questions or participate in any activities which make them uncomfortable. 3. The results of this study may be published or presented but the participant's identity and records will not be revealed unless required by Federal Law. A Federal Law allows the U.S. Food and Drug Administration, Office for Human Research Protections, Government Accountability Office and other Federal agencies, the Research and Development Committee, representatives of USAMRMC, Henry M. Jackson Foundation, the University of Health & Biological/Medical Application Form 11 Minnesota Institutional Review Board (IRB), and/or the Institutional Review Board (IRB)/Human Studies Subcommittee of the VA Medical Center to review records. Because of the need for these inspections, absolute confidentiality cannot be guaranteed. However, every effort would be made to minimize these risks by providing the participant with a unique numerical identifier at the beginning of the study in order to protect their actual identification and maintain complete confidentiality.*

5.3 Study Duration: *We plan on enrolling participants through May 2019. Data analysis should be completed by December 2019.*

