## **13.0 Risks to Participants**

- 13.1 Foreseeable Risks: *There is currently no evidence of serious side-effects associated with tDCS. Criteria for discontinuation that may rarely occur are sores at the tCS administration site, headaches that impair global functioning, and worsening psychosis. Mild side-effects that typically resolve upon discontinuation tDCS include light itching under the electrode at the beginning of administration, headache, fatigue, and nausea.*
- 13.2 Reproduction Risks: N/A

PROTOCOL TITLE:

VERSION DATE:

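### The optional 9 Hz visual tetanus is not covered by the protocol's risk text, and no eligibility criterion asks about known sensitivity to flickering or patterned light

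*Combined protocol and SAP*

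**What the plan says.** The study visits text in section 5.2 has two versions of the sensory task. After a visual search task, the session continues with "either a passive Auditory Oddball paradigm or a passive Visual Oddball paradigm", and a matching tetanus is given during stimulation. For the auditory form, "The auditory tetanus involves the presentation of a 1000Hz tone at a rate of 13Hz for a period of approximately 5min". For the visual form, "The visual tetanus involves the presentation of the visual stimulus (either a horizontal or vertical grating) at a rate of 9Hz"; no duration is attached to it. The two sessions are to be the same apart from active or sham tDCS.

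The Precautions part of 5.2 lists reasons for discontinuation linked to tDCS, cites earlier tDCS practice as reassurance, and states "No other risks are anticipated". Section 13.1 opens with "There is currently no evidence of serious side-effects associated with tDCS" and then lists tDCS effects. Neither section mentions the tetanus in either form.

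Section 8.1 requires normal hearing and no clinically significant head injury or neurological disease. Section 8.2 excludes "History of seizures or epilepsy" and, again, impaired hearing. Neither list has a criterion on vision or on reactions to light or pattern.

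**The concern.** Participants meet two experimental exposures, electrical stimulation and a rapid sensory stimulus. The risk and eligibility sections were written for the first. For the second, the eligibility list covers hearing, which suits the auditory version, and has no counterpart for the visual one.

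At stake is whether the blanket statement in 5.2 is supported for every procedure the protocol allows. Participants are healthy volunteers, and section 14.1 expects no benefit to them. The visual version also serves no stated purpose: the single aim concerns auditory cortex, the primary endpoint in 3.1 is the auditory evoked potential, and 3.2 lists no secondary endpoint. An exposure that answers no question in the protocol should at least be covered by its risk text.

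**Working it through.** The plan gives no figure to reproduce on this point, so the check is mainly a comparison of sections.

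1. **Is the visual tetanus a live procedure?** Yes. Section 5.2 offers it as an alternative to the auditory one, with its own stimulus and rate. It does not say who receives it or how many.

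2. **Does the risk text cover it?** No. Every harm named in 5.2 (Precautions) and 13.1 is tied to tDCS. The precedent cited in 5.2 concerns length of administration, current, electrode sponges and method of stimulation, all features of tDCS. Section 2.1 says that nobody has yet used this kind of sensory paradigm to study tDCS effects. The tDCS record therefore cannot by itself support a statement that no other risks exist when a visual tetanus is added. This shows the statement to be unsupported; it does not show a raised risk.

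3. **Does eligibility cover it indirectly?** In part. A person with a past seizure, an epilepsy diagnosis or a neurological disease is kept out by 8.1 and 8.2. A person who knows that flickering or patterned light affects them, but has none of those, meets every listed criterion.

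4. **Can the exposure be sized?** Only under an assumed duration. Presentations per session = 9 per second × 60 × minutes:
   - 2 min: 9 × 60 × 2 = 1,080
   - 5 min (the auditory figure, borrowed): 9 × 60 × 5 = 2,700
   - 10 min: 9 × 60 × 10 = 5,400

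   With two visual sessions these double to 2,160, 5,400 and 10,800. The session timeline does not settle the duration. Section 5.2 gives 10 min of simultaneous EEG and tDCS, starts the tetanus 15 min into stimulation, and ends both together. Those times conflict and must be reconciled in any case.

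5. **Can the risk be sized?** No. That would need the number receiving the visual version, the share of eligible adults who are sensitive, and the contrast, luminance and field size of the grating. The supplied text gives none of these. On the first, all that can be said is that the number lies between 0 and the 80 who may be consented under section 10.1.

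**The case against.** The strongest reply is that the documents report no harm from such a stimulus. Section 2.1 says that "a rapidly presented checkerboard pattern (a photic tetanus) can induce long lasting changes in evoked potentials", but that describes a checkerboard in earlier studies, and the changes are the plasticity effect of interest. A reader might infer that the protocol itself labels its grating a photic tetanus with lasting adverse effects. It does not. That the grating could provoke a reaction in a sensitive person is an assumption here, and how provocative it would be cannot be judged without the stimulus details. Section 5.2 refers to an instruments section that is not in the supplied text.

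General safeguards also exist. Participants may stop stimulation, may decline activities that make them uncomfortable (5.2) and may raise discomfort at any time (18.1). Section 23.1 places licensed medical professionals on the same floor at all three locations. These stand, but they act after discomfort begins. They replace neither a screening question nor an accurate risk statement.

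Three further inferences are tempting and fail:
- **That screening removes only people with past seizures.** An epilepsy diagnosis and neurological disease also bar entry.
- **That volunteers are not warned.** Consent pages were removed from the review copy and the screening script is not reproduced, so only the protocol's own silence can be shown.
- **That 13.1 also denies other risks.** The blanket sentence is in 5.2 alone; 13.1 simply omits the visual tetanus.

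Finally, the missing aim, endpoint and allocation for the visual version is arguably the more basic problem. That is fair: removing the version would close this point too.

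**Conclusion.** The point holds as a mismatch between sections. Section 5.2 allows a visual tetanus, the risk text in 5.2 and 13.1 does not address it, and 8.1 and 8.2 contain no criterion on known sensitivity to flickering or patterned light. Someone with that sensitivity and no barred diagnosis could be enrolled.

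Its importance is minor and its size is unknown. A reader might attach a probability of enrolling a sensitive participant, but this would rest on an assumed prevalence and on assuming that everyone receives the visual version, and the documents support neither. Even then it would be a chance of exposure, not of harm. The conclusion rests only on the protocol text as supplied. It does not depend on the presentation counts, and the power and analysis of the auditory endpoint are unaffected.

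**What to change.** First decide whether the visual version will be used.

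If it is kept:
- Add to 8.2 an exclusion for known sensitivity or adverse reaction to flickering or patterned light, and ask about it at email or phone screening.
- Correct the sentence in 5.2 that rules out other risks, so that it no longer extends tDCS experience to the visual task.
- Add the visual tetanus to 13.1 as a separate exposure.
- Check that the consent form and the screening script match.

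If it is not used, delete the visual oddball and visual tetanus from 5.2 instead. No stated aim or endpoint would be lost.

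The cost of keeping it is one screening question, a few sentences of protocol and possibly consent wording, and perhaps a few volunteers lost. A question about known sensitivity will not find people unaware of theirs, so it narrows the gap without fully closing it. The corrected risk wording is needed for that reason as well.
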